Thus, we aim to clarify whether HCQ relieves nonalcoholic steatohepatitis by reviewing medical records from our out-patient-clinic patients who accept the treatment of hydroxychloroquine (Plaquenil®).

A

B

Design : Retrospective study

Review medical records from patients who accept the treatment of hydroxychloroquine (Plaquenil®), find those with nonalcoholic steatohepatitis and observe the effects of hydroxychloroquine on them.

Methods :

Step 1 : screen out our targeted group : patients with nonalcoholic steatohepatitis

1. We have made a request to Information Technology Office of National Taiwan University Hospital, and this request is about the list of our out-patient-clinic patients who accept the treatment of hydroxychloroquine.
2. Collect and review the medical records, ultrasound and blood tests of patients in the abovementioned list and screen out those with nonalcoholic steatohepatitis based on the following criteria.

Inclusion criteria :

Our patients who taking hydroxychloroquine and match the following criteria

- A. Patients with fatty liver, based on the abdominal ultrasound report of which the date is the closest to the initial date of using HCQ.
- B. ALT level of 2.5 and 0.5 month prior to hydroxychloroquine treatment > 41 U/L
- C. With ALT result which is tested in 3 months after using HCQ.
- D. The initial date of taking HCQ is prior to September, 26, 2022, which is the date we got the list from Information Technology Office of National Taiwan University Hospital.

Exclusion criteria :

Our exclusion criteria can be separated into loose exclusion criteria and strict exclusion criteria.

Loose exclusion criteria : patients who match the following criteria will be excluded from the above group.

- A. Diseases of the biliary tract : the abdominal ultrasound report indicated the patient with stones in the biliary tract, or the patient with jaundice or his total bilirubin > 2.0 mg/dl
- B. Viral hepatitis : HBV Viral Load + or HCV Viral Load +
- C. Alcoholic steatohepatitis : History of drinking alcohol or AST/ALT > 1.5 and GGT > 2X
- D. Autoimmune hepatitis : ANA 1:80+ (above) or AMA+ anti-LKM+ or anti-SMA+
- E. Wilson's disease : ceruloplasmin < 20 mg/dl

Strict exclusion criteria : patients who had ever had viral hepatitis or was being infected by virus (HBV, HCV infection : HBsAg+ or anti-HBc+ or anti-HCV Ab+) will be further excluded from the above group.

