The definition of months : used in the criteria evaluation and the data analysis

Before patients used HCQ :

- 0.5 month : During the periods from one month prior to the date of initial use of HCQ to that date, we define the date which is the closest to 0.5 month as -0.5 month.
- 2.5 months : During the periods from four months to one month prior to the date of initial use of HCQ, we define the date which is the closest to 2.5 months as -2.5 months.
- 5.5 months : During the periods from seven months to four months prior to the date of initial use of HCQ, we define the date which is the closest to 5.5 months as -5.5 months.

After patients used HCQ :

- 0.75 months : During the periods that patients used HCQ for 0-1.5 months, we define the date which is the closest to 0.75 months as 0.75 months.
- 3 months : During the periods that patients used HCQ for 1.5-4.5 months, we define the date which is the closest to 3 months as 3 months.
- 6 months : During the periods that patients used HCQ for 4.5-7.5 months, we define the date which is the closest to 6 months as 6 months.
- 9 months : During the periods that patients used HCQ for 7.5-10.5 months, we define the date which is the closest to 9 months as 9 months.
- 12 months : During the periods that patients used HCQ for 10.5-13.5 months, we define the date which is the closest to 9 months as 12 months.

Then, in addition to the above-mentioned criteria, we will record the following two things separately.

The first one is hemochromatosis. Hemochromatosis may also cause hepatitis, but the prevalence of this disease in Taiwan is very low. Thus, we do not list hemochromatosis in the exclusion criteria.

The second one is drug-induced hepatitis. We do not list suspected drug-induced hepatitis in the exclusion criteria since drug-induced hepatitis may not be accurately confirmed based on our current medical records. However, if we find patients using drugs which may be related to hepatitis, we will record their information separately, including the duration of using these drugs and the ALT levels after stopping using it.

Step 2 : collect and analyze patients' medical information

(These patients are those with NASH and accept the treatment of HCQ)

We plan to collect the following information of each patients

1. The date when each patient started to take HCQ
2. Birth date :
To realize how old the patients were when they started to take HCQ.
3. Gender
4. Historical blood test results :

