 - A. ALT, AST, GGT, α -fetoprotein, platelet, FIB-4, WBC, bilirubin, albumin
 - a. For recording baseline demographics
 - b. To assess and analyze the status of hepatitis and liver fibrosis in each patient.
→ We plan to observe the ALT levels prior to the initial use of HCQ and ALT levels after it, and we will further analyze whether the ALT levels were decreased after patients took HCQ.
 - B. HbA1c*
 - a. For recording baseline demographics
 - b. To assess whether patients have diabetes mellitus
 - C. TG, TCHO*
 - a. For recording baseline demographics
 - b. To assess whether patients have hyperlipidemia

* We need these tests to realize whether patients have these comorbidities, since these are the risk factors of NASH.

Statistical Analysis Plan

1. We plan to use the statistical function of excel and Prism to analyze our results.
2. Initially, we will make the tables about the baseline demographics of patient who in our study group (patients with NASH and accept the treatment of HCQ), which we may use excel to help us arrange and analyze the tables.

- Then, we will check each patient's ALT levels in different month (prior to or after the initial use of HCQ), and we will use the date of initial use of HCQ as day0 and make box plots and violin plots to show the change of ALT levels with times going. We plan to use Prism to make the plots and analyze whether ALT levels were significantly decreased after patients took HCQ.

Members of our team

Position in this study	Name	Organizational Affiliation
Study Director	[name]	Graduate Institute of Pharmacology, College of Medicine, National Taiwan University
Study Principal Investigator	[name]., Ph.D.	1. Graduate Institute of Pharmacology, College of Medicine, National Taiwan University 2. Department of Internal Medicine, National Taiwan University Hospital

	Name	Organizational Affiliation	Phone and E-mail
Central Contact Person	[name]	Graduate Institute of Pharmacology, College of Medicine, National Taiwan University	[contact] E-mail : [contact]

References

- Pouwels, S., et al., *Non-alcoholic fatty liver disease (NAFLD): a review of pathophysiology, clinical management and effects of weight loss*. BMC Endocr Disord, 2022. **22**(1): p. 63.
- Niture, S., et al., *Emerging Roles of Impaired Autophagy in Fatty Liver Disease and Hepatocellular Carcinoma*. Int J Hepatol, 2021. **2021**: p. 6675762.

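### The single-group ALT test names no pre-HCQ reference or post-HCQ window, and two of the three candidate references are values on which patients were selected

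*Combined protocol and SAP*

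**What the plan says.** The study reviews the records of HCQ users only; there is no comparison group (Design; Methods, Step 1). Inclusion criterion B requires "ALT level of 2.5 and 0.5 month prior to hydroxychloroquine treatment > 41 U/L".

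The section on months is headed "The definition of months : used in the criteria evaluation and the data analysis", so the readings that qualify a patient are also analysis readings. It defines three pre-HCQ windows: −0.5, −2.5 and −5.5 months. The last is "During the periods from seven months to four months prior to the date of initial use of HCQ"; criterion B does not use it and no criterion requires it. Five post-HCQ windows follow: 0.75, 3, 6, 9 and 12 months.

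On the comparison itself, Step 2 (blood tests, item A) says only "We plan to observe the ALT levels prior to the initial use of HCQ and ALT levels after it". The Statistical Analysis Plan intends to "make box plots and violin plots to show the change of ALT levels with times going" and to "analyze whether ALT levels were significantly decreased after patients took HCQ". Day 0 there is a time origin, not an ALT value. No reference window, average or model is named, and no main post-HCQ window, test or significance level. Regression to the mean is not mentioned.

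**The concern.** A patient's ALT varies between readings. If patients enter because two readings were above a limit, those readings are on average above the patients' own usual level, and later readings drift back without treatment. A test for a fall from either reading counts that drift as drug effect.

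The stated objective is whether HCQ treats NASH effectively, and this before/after test is the only evidence planned. The Abstract already reads an early drop in liver enzymes as relief of steatohepatitis, which is the inference that this artefact can imitate. Because the reference is left open, two analysts following the plan could report different results from the same records.

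**Working it through.** The plan gives no sample size, SD, significance level or expected effect, so there is no figure of its own to reproduce. The check asks what criterion B does when HCQ has no effect.

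**From the documents:** one treated group; ALT > 41 U/L at −2.5 and −0.5 months; the month windows.

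**Assumed:** log ALT with between-patient SD 0.40; within-patient SD 0.10 to 0.35, with half the within-patient variance serially correlated (time constant 3 months) and half independent; source median 40 to 80 U/L; n = 50; paired t-test on log ALT, two-sided 5%, so 2.5% nominal for a false fall; outcome at +3 months.

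**1. Mechanism in closed form.** Suppose any two readings on a patient have the same correlation r. With M the source median and G the geometric mean of the reference reading among selected patients, the expected log change from a qualifying reading to any other time is −[(1 − r)/(1 + r)] × ln(G/M). For M = 60 and log-SD 0.5 (G by simulation):

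- r = 0.50, G = 75.5: −0.333 × 0.230 = −0.077, a fall of about 7.4%
- r = 0.70, G = 75.7: −0.176 × 0.232 = −0.041, a fall of about 4.0%
- r = 0.85, G = 75.3: −0.081 × 0.227 = −0.018, a fall of about 1.8%

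The −5.5 and +3 readings have equal geometric means in each case (69.9, 72.6 and 73.9), so the change from −5.5 is zero.

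**2. Simulation over the assumed grid, HCQ start unrelated to ALT.**

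| Reference | Change at +3 months | False significant falls, n = 50 |
|---|---|---|
| −0.5 | −0.2% to −12.5% | 3% to 57% |
| −0.5, middle case (median 60, within-SD 0.20) | −2.0% | 8% |
| Mean of −2.5 and −0.5 | about as −0.5 | 3% to 63% |
| −5.5 | under 1% | 2% to 3% |

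The −2.5 and −0.5 means agree within 0.2%, so −2.5 gives nearly the same fall as −0.5. The top figures need median 40 and within-SD 0.35. At n = 25 the −0.5 range is 3% to 32%. Drawing visit dates uniformly within the windows changed the falls by less than 0.5 percentage point.

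A second set of assumptions (source median 35, 45 or 60; log-SD 0.5; constant or decaying correlation) gives falls of 1.8% to 16.9% and 7% to 90% false significant falls with a qualifying reference, and 0% to 2.1% with −5.5.

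**3. Why −5.5 is nearly neutral only at about +3 months.** The −5.5 reading lies 3.0 and 5.0 months from the two qualifying readings. The +3 reading lies 3.5 and 5.5 months from them, so both are pulled up about equally. The 0.75-month reading is nearer (1.25 and 3.25) and the 12-month reading much further (12.5 and 14.5). In the top cell of the grid, −5.5 gives about +2.9% at 0.75 month and −3.2% at 12 months. With decaying correlation, the second set gives +3.2% to +8.6% and −5.5% to −22.8%.

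**4. If ALT influenced the HCQ start** (further assumptions; change at +3 months, false falls in brackets):

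| Assumed trigger | From −0.5 | From −2.5 | From −5.5 |
|---|---|---|---|
| Rise: −0.5 at least 1.2 times −2.5 | −10% to −28% (about 98% or more) | +8% to +23% (about 0%) | +3% to +5% (at most 0.6%) |
| All three values > 41 | close to −5.5 | close to −5.5 | −0.1% to −10% (3% to 39%) |
| All three values > 60 | close to −5.5 | close to −5.5 | −0.4% to −15% (4% to 73%) |

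In the last two rows the three pre-HCQ means differ by only about 1%. Requiring a significant fall from both −0.5 and −5.5 holds false claims to at most 3% when the start is unrelated to ALT and 0.6% after a rise, but they reach 26% (all > 41) and 65% (all > 60) after sustained elevation.

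**5. Price of the −5.5 comparison.** Noncentral t with noncentrality ln(1/0.8) × √n / SD of the change. For a true 20% fall and SD 0.487 (within-SD 0.35, median 60): n = 50 gives 0.223 × 7.07 / 0.487 = 3.24, power 89%. If only 25 have a −5.5 value, 0.223 × 5 / 0.487 = 2.29, power 59%. At within-SD 0.20 (SD of the change 0.279) the figures are over 99% and 97%.

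**The case against.** The sizes illustrate a mechanism and do not measure it in this cohort. The middle case is a 2% fall with 8% false falls. With a 12-month time constant the top cell drops from about 58% to 31–40%, while the second set of assumptions reaches 90%. This stands: only the direction of the criterion B bias is firm.

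The planned plots would show the pre-HCQ windows side by side. That helps a reader, but it does not settle which reading the test uses.

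The Abstract suggests that at least some patients received HCQ for their liver disease, which sits closer to sustained elevation than to a start unrelated to ALT. There −5.5 protects little: in the top cell about 40% false falls against 43% from −0.5 (all > 41), and 74% against 80% (all > 60). This stands, and with the loss of power it is why −5.5 should not be the sole main test. The ALT trigger is nevertheless unstated, and the list covers all the clinic's HCQ users.

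Early results had already been seen (Abstract), so naming the reference now is not true prespecification. This also stands.

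Three stronger readings are tempting and unsupported:

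- A reader might infer that the direction of the bias generally depends on the reference. Criterion B alone pushes −2.5 and −0.5 the same way. The sign turns on the reference only if a rise in ALT prompted the start, which the documents do not say.
- A reader might infer that any fall found would be an artefact. With otherwise stable ALT, the artefact would not explain a large fall.
- A reader might find criterion C, "With ALT result which is tested in 3 months after using HCQ", ambiguous. The month definitions apply to the criteria, so it most naturally means the window "During the periods that patients used HCQ for 1.5-4.5 months".

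**Conclusion.** The point holds in this form. Patients are selected on ALT at −2.5 and −0.5 months, and the plan tests for a fall without naming the reference or the post-HCQ window and without addressing regression to the mean. If ALT is otherwise stable and the start was unrelated to it, a reference of −2.5, −0.5 or their mean leans towards a fall with no drug effect. The extent rests wholly on assumed ALT variability, source median and n, and it shrinks as patients lie further above 41 U/L. The −5.5 window escapes criterion B, nearly so in effect at about +3 months, but it does not escape the decision to prescribe. This should be fixed before a fall in ALT is offered as evidence that HCQ treats NASH.

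**What to change.** 1. In the SAP, name the pre-HCQ reference and one main post-HCQ window, for example 3 months (1.5 to 4.5), for which criterion C already requires a value. Beside any comparison with −2.5 or −0.5, report the within-patient change in log ALT from −5.5 months, and do not claim a fall unless it agrees. Define agreement; the version checked above was a significant fall from both. Label the −2.5 and −0.5 comparisons as subject to regression to the mean. State that −5.5 is nearly free of criterion B bias at about +3 months, not at every window. State also that it remains biased against HCQ if the start followed a rise, and towards HCQ if it followed sustained elevation.

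2. Report how many patients have a −5.5 value, how they differ from those without one, and mean log ALT at all three pre-HCQ windows. A clearly higher −0.5 mean would suggest a start after a rise. Near-equal means are not reassurance, because sustained elevation looks the same.

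3. Limit the conclusion: ALT fell after HCQ start, and without an untreated group this cannot be separated from regression to the mean or natural course. State that the reference was chosen after early results had been seen.

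All of this is wording on data already planned. The downside is that patients without a −5.5 value drop out of that comparison, possibly selectively. If agreement means significance, a claim can have no more power than the −5.5 comparison has. It should therefore be a required companion, not the sole main test.

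### Inclusion criterion B sets no minimum gap between its two pre-HCQ ALT values, so a short ALT rise in a patient with fatty liver can enter and its recovery adds to the before-after fall

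*Combined protocol and SAP*

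**What the plan says.** In Methods, Step 1, inclusion criterion B asks for "ALT level of 2.5 and 0.5 month prior to hydroxychloroquine treatment > 41 U/L". The section on months states its own scope: "The definition of months : used in the criteria evaluation and the data analysis". The windows therefore decide eligibility as well as the plotted time points.

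- The -0.5 month value is sought "During the periods from one month prior to the date of initial use of HCQ to that date".
- The -2.5 month value is sought "During the periods from four months to one month prior to the date of initial use of HCQ".
- Within a window the draw nearest the nominal time is used; for the earlier one, "we define the date which is the closest to 2.5 months as -2.5 months". The -0.5 month window has a matching rule.
- A -5.5 month value is also defined ("During the periods from seven months to four months prior to the date of initial use of HCQ"), but criterion B does not require it.

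Other entry rules bear on the point. Criterion A requires "Patients with fatty liver, based on the abdominal ultrasound report of which the date is the closest to the initial date of using HCQ". The loose exclusions remove patients with jaundice or total bilirubin above 2.0 mg/dl, and those with a positive HBV or HCV viral load. On drug injury the plan says "We do not list suspected drug-induced hepatitis in the exclusion criteria", but it will record suspect drugs separately, with duration of use and ALT after stopping. The Statistical Analysis Plan then asks whether ALT fell after HCQ in this one treated group.

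**The concern.** Two raised values about two months apart would be reasonable evidence of persistent hepatitis. Two raised values a few days apart are close to a single observation. If the rule accepts the second while its labels suggest the first, some patients may enter during a time-limited ALT rise.

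Such a rise settles by the 3-month window (1.5 to 4.5 months on HCQ) with or without the drug. With no comparator, the analysis cannot separate that recovery from an HCQ effect, and the error favours HCQ. Nothing else among the entry rules establishes duration. Ultrasound shows steatosis, not the cause or length of the ALT rise; the viral exclusion covers HBV and HCV only; the -5.5 month value is optional; and no analysis is planned that uses the separate record of suspect drugs.

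**Working it through.** The documents give no sample size, ALT variability or testing frequency, so there is no stated figure to reproduce. Only step 1 rests on the documents alone.

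**1. Allowed gap.** The windows are 4 to 1 months and 1 to 0 months before HCQ. Minimum gap = 1 − 1 = 0 months; maximum = 4 − 0 = 4 months. Draws on days -32 and -29 qualify, as do draws on days -33 and -14 (19 days apart), provided no draw nearer the nominal time displaces them.

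**2. How often gaps are short (assumed test dates).** With one uniformly dated draw per window, P(gap < g) = (g − 0.5)/3 for g from 1 to 3 months:
- under 1 month: 0.5/3 = 16.7%
- under 8 weeks (1.84 months): 1.34/3 ≈ 45%
- under 2 months: 1.5/3 = 50%

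With random (Poisson) test dates and the closest-date rule, simulated gaps under one month are:

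| Tests per month | Pairs under 1 month apart |
|---|---|
| 1/3 | 12.3% |
| 0.5 | 10.0% |
| 1 | 5.4% |
| 2 | 1.2% |

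**3. What one such patient contributes (assumed illness).** Take usual ALT 30 U/L, a peak of 150 on day -33, excess halving every 2 weeks, and no drug effect: ALT(t) = 30 + 120 × 0.5^(t/14 days).
- Day -33 (t = 0): 150
- Day -14 (t = 19): 76.8
- Day 91 (t = 124): 30.3

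Both entry values exceed 41, and the fall from the -0.5 month value is about 61%. If a share f of the cohort behaves this way and nobody else changes, the geometric-mean fall is 1 − exp(−f × ln(76.8/30.3)): 4.6%, 8.9% and 17.0% for f = 5%, 10% and 20%. These shares are purely illustrative.

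**4. How long such a rise stays above 41.**
- Peak 150, 2-week half-life: 2 × log2(120/11) = 6.9 weeks
- Peak 300, 2-week half-life: 2 × log2(270/11) = 9.2 weeks
- Peak 150, 3-week half-life: 3 × log2(120/11) = 10.3 weeks

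An 8-week gap stops the first; the other two can outlast it.

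**5. What a minimum gap does for brief episodes.** The table gives the chance that, when the -0.5 month draw falls in an episode, the -2.5 month draw falls in it too and the pair meets the gap rule. It assumes one uniformly dated draw per window and random episode timing.

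| Episode length | No gap rule | 1 month | 2 months |
|---|---|---|---|
| 1 month | 5.6% | 0% | 0% |
| 2 months | 19.4% | 8.4% | 0% |
| 3 months | 35.2% | 22.2% | 5.5% |

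**6. What a minimum gap does for regression to the mean.** I simulated ALT with no drug effect and no illness episodes: median 35 U/L, log-scale SD 0.40 between and 0.35 within patients, correlation time 0.5 to 2 months, entry if both values exceed 41. The spurious fall from -0.5 to +3 months is 15.6–16.5% with no gap rule and 14.7–15.3% with a two-month gap. The gap rule barely touches this bias.

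**The case against.** The strongest reply is that the plan already steers away from close pairs. The closest-date rule pulls the two draws towards two months apart, and a close pair is selected only when the windows hold no better-placed draw. This stands: short gaps should be a minority. The rule does not help a recently referred patient with one draw per window.

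A reader might infer that any brief hepatitis is labelled NASH here. The documents do not support that. Fatty liver on ultrasound is required, icteric illness is removed by the jaundice and bilirubin exclusion, HBV and HCV are screened, and suspect drugs are recorded. What remains is a short, non-icteric rise in a patient with steatosis.

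A reader might also infer that recovery is automatically credited to HCQ. The plan plots ALT at each time point before and after day 0 and names no single baseline, so a fall already under way before HCQ (150 to 77 in the example) could show in the plots. That helps, but the planned question is still whether ALT fell after HCQ, and no rule says how a pre-start decline would be handled.

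Finally, one could argue that the gap is secondary to selecting on raised ALT without a comparator. That is correct, and step 6 shows it. But that simulation models fluctuation around a stable level, not a discrete illness; for discrete episodes step 5 shows the gap does matter.

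**Conclusion.** The concern holds in a limited form. It is certain from the text that the windows meet at one month, that no minimum interval exists, and that one draw exactly one month before HCQ could be read as meeting both parts of criterion B. It follows that a short, non-icteric ALT rise in a patient with fatty liver can enter and add a fall unrelated to HCQ.

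The size is not known. Gaps under one month run from about 1% to 17% of pairs on assumed test dates, and the documents do not show how many of those patients would have a transient rise. The 61% individual fall and the 5–17% cohort falls depend wholly on assumed values.

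Two stronger conclusions are not supported. One is that the touching windows are the main source of bias: selection on ALT > 41 U/L without a comparator is the larger problem, and a gap rule leaves it almost unchanged. The other is that an 8-week gap should define the main cohort. With one uniformly dated draw per window that would remove about 45% of pairs, including patients whose -5.5 month value already shows persistence, and it would still admit rises lasting longer than 8 weeks.

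**What to change.** 1. Add to criterion B that the -2.5 and -0.5 month values must come from two different draws, and assign the one-month date to one window only. Keep the cohort otherwise as defined.
2. Record the gap in days between the two draws for every patient and report its distribution.
3. Pre-specify a sensitivity analysis repeating the ALT comparison in patients with documented persistence: draws at least 8 weeks apart, or ALT also > 41 U/L at -5.5 months. The second route puts at least 4 − 1 = 3 months between the oldest and newest raised values. Report short-gap patients separately.
4. State in advance that if the fall shrinks in the persistent subset, the conclusion will be limited accordingly.

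The cost is a sentence or two in the protocol and a date check on ALT values the study already plans to review. The downside is a smaller, less precise subset for the sensitivity analysis, and rises lasting longer than 8 weeks can still pass the gap rule. None of this addresses regression to the mean, which needs separate treatment through a comparator or a dedicated analysis.

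### The viral, autoimmune and Wilson's exclusions act only on an abnormal finding on record, so a never-tested, never-diagnosed patient stays in both the loose and strict sets and is labelled NASH

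*Combined protocol and SAP*

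**What the plan says.** The study is a retrospective chart review. Methods, Step 1 tells the team to "Collect and review the medical records, ultrasound and blood tests of patients in the abovementioned list" and to pick out the NASH patients by the listed criteria.

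Apart from a start-date cut-off, the inclusion criteria ask for three things:
- "Patients with fatty liver, based on the abdominal ultrasound report of which the date is the closest to the initial date of using HCQ"
- "ALT level of 2.5 and 0.5 month prior to hydroxychloroquine treatment > 41 U/L"
- "With ALT result which is tested in 3 months after using HCQ"

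The loose exclusions then apply as follows: "patients who match the following criteria will be excluded from the above group". Criterion B (viral) is "HBV Viral Load + or HCV Viral Load" positive. Criterion D (autoimmune) is an ANA of 1:80 or above, or other positive autoantibodies (AMA, anti-LKM, anti-SMA). Criterion E (Wilson's disease) is "ceruloplasmin < 20 mg/dl".

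The strict exclusion further removes patients with past or current viral hepatitis, with the markers given as "HBsAg+ or anti-HBc+ or anti-HCV Ab" positive. It adds nothing on autoimmune or Wilson's disease.

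Step 2 and the Statistical Analysis Plan then treat the retained patients as the NASH group and compare ALT before and after HCQ. No comparison group is described.

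**The concern.** NASH is defined here by fatty liver on ultrasound, raised ALT and the absence of other causes. That absence is established only by failing to find an abnormal result. In a chart review, no abnormal result can mean a normal test or no test at all, and the rules do not separate the two.

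The study's conclusion concerns ALT in NASH. With no control group, attributing an ALT fall to an effect on NASH depends on the cohort being what it is called. If some retained patients have another hepatitis, the result describes a mixed group, and nothing in the planned output would show how mixed it is.

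**Working it through.** The plan states no sample size, testing coverage or marker prevalence, so there is no figure to reproduce. The check is a reading of the rules, followed by an illustration on assumed values.

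**Step 1: which criteria require a result to exist.** Both pre-treatment ALT values must exceed 41 U/L, so they must exist. The on-treatment ALT is required outright, and the ultrasound report is needed to establish fatty liver. No inclusion criterion mentions viral load, viral serology, autoantibodies or ceruloplasmin.

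**Step 2: an untested patient under the rules as written.**

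| Patient | Loose set | Strict set |
|---|---|---|
| No viral test, no viral diagnosis on record | kept | kept |
| No autoantibody test, no diagnosis on record | kept | kept |
| No ceruloplasmin, no diagnosis on record | kept | kept |
| HBsAg+ or anti-HCV+, no viral load on record | kept | removed |

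The biliary and alcohol criteria also use ultrasound, jaundice or drinking history, so they are outside this point.

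**Step 3: would the planned output reveal it?** The Step 2 data list covers liver enzymes, α-fetoprotein, blood counts, FIB-4, bilirubin, albumin, HbA1c and lipids. It has none of the viral, autoantibody or ceruloplasmin tests. The markers are looked at during screening, but no count of patients tested is planned.

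**Step 4: illustration for one cause.** Let u be the untested share of otherwise eligible patients and p the share who would be positive. Assume an error-free test and testing unrelated to status. Per eligible patient, the rule removes (1 − u)p and keeps 1 − (1 − u)p, of which up is positive but undetected:

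undetected share of the retained cohort = up / (1 − (1 − u)p)

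With u = 0.50 and p = 0.10: 0.05 / (1 − 0.05) = 0.05 / 0.95 = 5.3%. Other assumed values give:

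| p | u = 10% | u = 30% | u = 50% |
|---|---|---|---|
| 5% | 0.5% | 1.6% | 2.6% |
| 10% | 1.1% | 3.2% | 5.3% |
| 20% | 2.4% | 7.0% | 11.1% |

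Over a wider assumed range, u = 20% with p = 2% gives 0.004 / 0.984 = 0.4%, and u = 80% with p = 15% gives 0.12 / 0.97 = 12.4%. With u = 0 the share is 0%.

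These are shares of marker-positive patients. A patient who would test at ANA 1:80 does not necessarily have autoimmune hepatitis, so the share with the disease may be lower. The values should not be added across causes, because the same u and p are unlikely to hold for each.

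**The case against.** The strongest reply is that the plan is silent on missing tests, and silence is not a rule. The investigators may have had these tests on nearly everyone. The Abstract compares ANA-negative with weakly ANA-positive patients, so ANA was on record for at least some. This stands as a limit on size: the documents do not show that many patients were untested. It does not remove the gap, because exclusion by match, with no missing-test rule, keeps an untested patient.

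The strict rule's reference to past viral hepatitis can also catch a diagnosis noted in the chart without a serology result. That is correct, and it is why the point is limited to patients neither tested nor diagnosed.

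The strict set concerns viral hepatitis only, and it does remove the serology-positive patient without a viral load. Both are fair, so its silence on autoimmune and Wilson's disease is not a failure of its own purpose. It still keeps patients with no viral serology, and that does bear on its purpose.

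Two stronger readings are tempting. A reader might infer that untested autoimmune patients push the result upward, since the Abstract says HCQ has therapeutic effects in autoimmune disorders. That statement is general and not about autoimmune hepatitis, and the Abstract also reports similar effects in ANA-negative and weakly ANA-positive patients. That report is uncontrolled and covers weak positivity only, so the bias is possible but not shown. A reader might also infer that a planned loose-versus-strict contrast is defeated. The Statistical Analysis Plan refers to a single study group and plans no such contrast.

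**Conclusion.** The point holds as a defect in how the cohort is defined. For viral, autoimmune and Wilson's disease, exclusion needs an abnormal finding on record and no criterion requires the tests. Never-tested, never-diagnosed patients therefore stay in both sets under the NASH label, and the loose set also keeps known HBsAg-positive or anti-HCV-positive patients who have no viral load on record.

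The size cannot be determined from the documents. The 5.3% figure rests on assumed values of 50% untested and 10% positive, an error-free test, and testing unrelated to status. Coverage could be near complete, in which case the effect is negligible. The documents do not establish a direction of bias. The change is worth making because, without the counts, a reader cannot tell a clean cohort from an unexamined one.

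**What to change.** 1. Keep all current exclusions, including anti-HBc.
2. Code every listed exclusion test as positive, negative or not tested, and report the not-tested count for each criterion. This also identifies the serology-positive patients in the loose set who have no viral load on record.
3. Admit patients to the strict set only with documented negative HBsAg, anti-HBc and anti-HCV Ab.
4. Repeat the ALT analysis in patients with documented non-excluding results on the listed viral, autoantibody and ceruloplasmin tests. If few have all of them, require at least viral serology and ANA.
5. Show the full-cohort result alongside.

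The cost is a change of wording and a three-level code in a chart review already planned, with no new patient contact. The strict set and the fully tested set will be smaller, by an amount the documents do not allow one to estimate. Fully tested patients may also differ from the rest, for example if clinicians tested those they suspected, so the restricted result should accompany the full-cohort result and not replace it.
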